**NOTES:**

- If the study treatment stop date is missing, then the AE will be considered to be treatment emergent.
- Time of study treatment dosing and start/stop time of AEs should be considered, if collected.

**9.3.1.2. Study Phases for Concomitant Medication**

The study phase for concomitant medication will be categorized into pre-treatment, period 1, period 2, period 3, and period 4 based on medication start date and time.

Study Phase	Definition
Pre-Treatment	Start Date and Time < Dosing Date in Period 1
Period 1	Dosing Date in Period 1 ≤ Start Date and Time < Dosing Date in Period 2
Period 2	Dosing Date in Period 2 ≤ Start Date and Time < Dosing Date in Period 3
Period 3	Dosing Date in Period 3 ≤ Start Date and Time < Dosing Date in Period 4
Period 4	Dosing Date in Period 4 ≤ Start Date and Time

**NOTES:**

- Please refer to [Appendix 6: Reporting Standards for Missing Data](#) for handling of missing and partial dates for concomitant medication. Use the rules in this table if concomitant medication date is completely missing.

## 9.4. Appendix 4: Data Display Standards & Handling Conventions

### 9.4.1. Reporting Process

Software	

 
The currently supported versions of SAS software [Insert Other Software as Required] will be used.
 
	
Reporting Area	
HARP Server	: N/A
HARP Compound	: N/A
Analysis Datasets	

 
Analysis datasets will be created according to CDISC standards (SDTM IG Version 3.2 & ADaM IG Version 1.0).
 
	
Generation of RTF Files	

 
RTF files will be generated.
 
	

### 9.4.2. Reporting Standards

General	

 
The current GSK Integrated Data Standards Library (IDSL) will be applied for reporting, unless otherwise stated (IDSL Standards Location: https://spope.gsk.com/sites/IDSLLibrary/SitePages/Home.aspx):           
 
4.03 to 4.23: General Principles
 
5.01 to 5.08: Principles Related to Data Listings
 
6.01 to 6.11: Principles Related to Summary Tables
 
7.01 to 7.13: Principles Related to Graphics
 
 
 
Do not include subject level listings in the main body of the GSK Clinical Study Report. All subject level listings should be located in the modular appendices as ICH or non-ICH listings
 
	
Formats	

 
GSK IDSL Statistical Principles (5.03 & 6.06.3) for decimal places (DP's) will be adopted for reporting of data based on the raw data collected, unless otherwise stated.
 
Numeric data will be reported at the precision collected on the eCRF.
 
The reported precision from non eCRF sources will follow the IDSL statistical principles but may be adjusted to a clinically interpretable number of DP's.           
 
For [Insert Endpoint / Parameter] the following DP's places will be applied:
 
Summary Statistics:
 
Listings:
 
 
 
	
Planned and Actual Time	

 
Reporting for tables, figures and formal statistical analyses:           
 
Planned time relative to dosing will be used in figures, summaries, statistical analyses and calculation of any derived parameters, unless otherwise stated.
 
The impact of any major deviation from the planned assessment times and/or scheduled visit days on the analyses and interpretation of the results will be assessed as appropriate.
 
 
 
Reporting for Data Listings:           
 
Planned and actual time relative to study drug dosing will be shown in listings (Refer to IDSL Statistical Principle 5.05.1).
 
Unscheduled or unplanned readings will be presented within the subject's listings.
 
 
 
	

Unscheduled Visits	

 
Unscheduled visits will not be included in summary tables and/or figures.
 
All unscheduled visits will be included in listings.
 
	
Descriptive Summary Statistics	
Continuous Data	Refer to IDSL Statistical Principle 6.06.1
Categorical Data	N, n, frequency, %
Graphical Displays	

 
Refer to IDSL Statistical Principles 7.01 to 7.13.
 
[Insert as Required: If any publication related displays have been specified, please provide relevant details]
 
	

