### 5.2. Baseline Definitions

Baseline definitions are applied to each period.

For all endpoints (except as noted in baseline definitions) the baseline value will be the latest pre-dose assessment with a non-missing value, including those from unscheduled visits. If time is not collected, Day 1 assessments are assumed to be taken prior to first dose and used as baseline.

Unless otherwise stated, if baseline data is missing no derivation will be performed and baseline will be set to missing.

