##### Laboratory Data Shifts from Baseline Relative to PCI Criteria

The number and percentage of subjects with laboratory results within each PCI criteria category (Low, W/in Range, High) during each planned time assessment will be summarized by treatment group relative to their baseline category by laboratory test, where PCI criteria are available. The percentages are based on the number of subjects in the treatment group with data for the laboratory test at the specified planned time (n). The worst case post-baseline is used to summarize the subjects' overall worst case shifts during the post-baseline period.

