### 9.3. Appendix 3: Study Phases and Treatment Emergent Adverse Events

#### 9.3.1. Study Phases

Assessments and events will be classified according to the time of occurrence relative to the date of dosing date.

Study Phase	Definition
Pre-Treatment	Date $\leq$ Previous Day of Dosing Date in Period 1
Period 1	Previous Day of Dosing Date in Period 1 $\leq$ Date $<$ Previous Day of Dosing Date in Period 2
Period 2	Previous Day of Dosing Date in Period 2 $\leq$ Date $<$ Previous Day of Dosing Date in Period 3
Period 3	Previous Day of Dosing Date in Period 3 $\leq$ Date $<$ Previous Day of Dosing Date in Period 4
Period 4	Previous Day of Dosing Date in Period 4 $\leq$ Date

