## 9.5. Appendix 5: Derived and Transformed Data

### 9.5.1. General

Multiple Measurements at One Analysis Time Point	

 
Mean of the measurements will be calculated and used in any derivation of summary statistics but if listed, all data will be presented.
 
Participants having both High and Low values for Normal Ranges at any post-baseline visit for safety parameters will be counted in both the High and Low categories of “Any visit post-baseline” row of related summary tables. This will also be applicable to relevant Potential Clinical Importance summary tables.
 
	
Study Day	

 
Calculated as the number of days from First Dose Date: 
 
Ref Date = Missing → Study Day = Missing
 
Ref Date < First Dose Date → Study Day = Ref Date - First Dose Date
 
Ref Date ≥ First Dose Date → Study Day = Ref Date - (First Dose Date) + 1
 
 
 
	
Period Day	

 
Calculated as the number of days from Dosing Date in each period. For study phase derivation, see Appendix 3. 
 
If Study Phase of Ref Assessment or Event = Pre-Treatment or Missing → Period Day = Missing
 
If Study Phase of Ref Assessment or Event = Period X and Ref Date is on or after Dosing Date in Period X → Period Day = Ref Date - Dosing Date in Period X + 1 day
 
If Study Phase of Ref Assessment or Event = Period X and Ref Date is before Dosing Date in Period X → Period Day = Ref Date - Dosing Date in Period X
 
 
 
 
Note: X takes a value of 1, 2, 3, 4.
	

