## 9.6. Appendix 6: Reporting Standards for Missing Data

### 9.6.1. Premature Withdrawals

Element	Reporting Detail
General	
 
Subject study completion (i.e. as specified in the protocol) was defined as completion of all phases of the study including the last visit or the last scheduled procedure.
 
Withdrawn subjects may be replaced in the study.
 
All available data from participants who were withdrawn from the study will be listed and all available planned data will be included in summary tables and figures, unless otherwise specified.
 
Withdrawal visits will be slotted as per Appendix 3: Assessment Windows or will be summarised as withdrawal visits.
 

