### 9.9.5. Safety Tables

Safety: Tables					
No.	Population	IDSL / Example Shell	Title	Programming Notes	Deliverable [Priority]
Adverse Events (AEs)					
2.1.	Safety	AE1CP	Summary of All Adverse Events by System Organ Class and Preferred Term	ICH E3	SAC
2.2.	Safety	AE5A	Summary of All Adverse Events by Maximum Intensity by System Organ Class and Preferred Term	ICH E3	SAC
2.3.	Safety	AE1CP	Summary All Drug-Related Adverse Events by System Organ Class and Preferred Term	ICH E3 .	SAC
2.4.	Safety	AE5A	Summary of All Drug-Related Adverse Events by System Organ Class and Preferred Term and Maximum Intensity	ICH E3 .	SAC
Laboratory: Chemistry					
2.5.	Safety	LB1	Summary of Chemistry Values		SAC
2.6.	Safety	LB1	Summary of Chemistry Changes from Baseline	ICH E3	SAC
2.7.	Safety	LB4	Summary of Chemistry Data Shifts from Baseline Relative to PCI Criteria	ICH E3	SAC
Laboratory: Hematology					
2.8.	Safety	LB1	Summary of Hematology Values		SAC
2.9.	Safety	LB1	Summary of Hematology Changes from Baseline	ICH E3	SAC
2.10.	Safety	LB4	Summary of Hematology Data Shifts from Baseline Relative to PCI Criteria	ICH E3	SAC

CONFIDENTIAL

205037

Safety: Tables					
No.	Population	IDSL / Example Shell	Title	Programming Notes	Deliverable [Priority]
Laboratory: Urinalysis					
2.11.	Safety	LB1	Summary of Urinalysis Data (Gravity and pH)		SAC
2.12.	Safety	LB1	Summary of Urinalysis Concentration Change from Baseline (Gravity and pH)	ICH E3	SAC
2.13.	Safety	UR3b	Summary of Urinalysis Data (Glucose, Protein, Blood, Ketones, Bilirubin, Urobilinogen)		SAC
Neurological Examination					
2.14.	Safety	NE1	Summary of Neurological Examination		SAC
ECG					
2.15.	Safety	EG1	Summary of ECG Findings	IDSL	SAC
2.16.	Safety	EG2	Summary of ECG Values		SAC
2.17.	Safety	EG2	Summary of Change from Baseline in ECG Values by Visit	IDSL	SAC
2.18.	Safety	HM1	Summary of Cardiac Telemetry	IDSL	SAC
2.19.	Safety	HM2	Summary of Cardiac Telemetry Abnornormalities	IDSL	SAC
Vital Signs					
2.20.	Safety	VS1	Summary of Vital Signs	IDSL	SAC
2.21.	Safety	VS1	Summary of Change from Baseline in Vital Signs	ICH E3	SAC

CONFIDENTIAL

205037

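### SAP 9.4.2 keeps unscheduled labs out of summary tables with no exception for the worst-case shift row, which for completers then repeats the 72 hr row in 36 of 48 subject-periods

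*SAP*

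**What the plan says.** SAP 9.4.2, under Unscheduled Visits, reads: "Unscheduled visits will not be included in summary tables and/or figures". No exception is given. Unscheduled values are sent to listings, and the same section says under Planned and Actual Time: "Unscheduled or unplanned readings will be presented within the" subject's listings. For withdrawn subjects, SAP 9.6.1 says that "all available planned data will be included in summary tables and figures", which again points to planned data only.

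SAP 7.2.1 describes the laboratory shift tables. They are built by planned time, with one further summary of each subject's "overall worst case shifts during the post-baseline period". The displays concerned are Table 2.7, "Summary of Chemistry Data Shifts from Baseline Relative to PCI Criteria", and its haematology counterpart, Table 2.10.

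Two other rules bear on this. SAP 5.2 says that "the baseline value will be the latest pre-dose assessment with a non-missing value, including those from unscheduled visits", so unscheduled values may set the reference for a shift. SAP 9.5.1 averages multiple measurements at one time point, and says that participants with both high and low values "at any post-baseline visit for safety parameters will be counted in both the High and Low categories" of the any-visit row. That provision presupposes more than one post-baseline value per subject.

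**The concern.** A reader of a row labelled worst case would take it to cover every value after dosing. Under 9.4.2 it covers scheduled values only, and this schedule has very few. An abnormality that appears only at an unscheduled draw would not register in the by-dose counts, although an unscheduled pre-dose value could have set the baseline.

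Such draws are foreseen. Protocol 9 allows repeat or unscheduled samples for safety or technical reasons. Protocol 9.3.5 calls for clinically significant abnormal tests to be repeated, and Appendix 7 requires repeat liver chemistries. The sentinel review in Protocol 5.3 includes clinical labs and may close 24 hr after the third dose, at 14 + 24 = 38 hr. If labs are drawn for a review held before 72 hr, they are unscheduled as well.

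What is at stake is the accuracy of one safety display, not the conduct of the trial. No escalation or stopping rule uses these rows.

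**Working it through.** **Inputs**
- Four sequences of 3 subjects each (Protocol 5.1).
- Haematology and chemistry on Day -1 and at 72 hr in each period, plus one follow-up draw (Protocol 2; the SAP 9.2.1 copy agrees).
- Period boundaries (SAP 9.3.1): each period starts on the day before its dosing day, so a Day -1 draw belongs to the period that it opens. Period 4 has no upper bound, so follow-up falls in it.
- Assumption: all 12 subjects complete and none is replaced.

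**Step 1. Scheduled post-dose labs per subject-period.** Periods 1-3: one (72 hr). Period 4: two (72 hr and follow-up).

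**Step 2. Count by treatment.**

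| Treatment | Subject-periods in Periods 1-3 | In Period 4 | Only the 72 hr lab | Scheduled post-dose draws |
|---|---|---|---|---|
| 60 mg | 9 + 3 = 12 | 0 | 12/12 | 12 x 1 = 12 |
| 120 mg | 6 + 6 = 12 | 0 | 12/12 | 12 x 1 = 12 |
| Placebo | 3 + 3 + 3 = 9 | 3 | 9/12 | 9 x 1 + 3 x 2 = 15 |
| 240 mg | 3 | 9 | 3/12 | 3 x 1 + 9 x 2 = 21 |
| Total | 36 | 12 | 36/48 | 60 |

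**Step 3. Consequence.** The worst of a single value is that value. For completers the worst-case row therefore equals the 72 hr row throughout 60 mg and 120 mg. It can differ only through the follow-up draw, for 3 placebo subjects and 9 subjects at 240 mg.

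**Step 4. Which unscheduled values matter.**
- A repeat of a test already flagged at 72 hr adds no new shift in that direction.
- A repeat assigned to the 72 hr time point is averaged under 9.5.1, and the worst-case row still equals the 72 hr row.
- A valid value out of range only at another draw is absent from the row. This is the gap.

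**Step 5. What one such subject would do.** Protocol 10.1 gives exact 95% upper limits of 26.5% for 0/12 and 38.5% for 1/12. Both reproduce: 1 - 0.025^(1/12) = 26.5%, and the 97.5% point of Beta(2, 11) is 38.5%. A subject whose only out-of-range value is unscheduled would move a cell from 0/12 to 1/12, and the limit from 26.5% to 38.5%. This illustrates one case. It is not a predicted frequency, because the documents give no rate of unscheduled out-of-range labs.

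**The case against.** The strongest reply is that the SAP is coherent as it stands. Section 7.2.1 counts results at planned times and takes percentages over subjects with data at the planned time, and 9.4.2 sets planned time as the default for summaries. The row can be read as the worst case over scheduled assessments. That is a fair reading, and a reader who infers a direct contradiction goes too far: 7.2.1 never says that unscheduled values enter. What remains is that, on this reading, the row tells the reader nothing new for 60 mg and 120 mg.

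Three further inferences are not supported.
- *The row always understates the true worst case.* Protocol 9 foresees technical problems with samples, and a spurious 72 hr value would make a scheduled-only row overstate it.
- *Safety data are lost.* Listings 21-26 show the values, including the potential-clinical-importance (PCI) Listings 22, 23, 25 and 26. Clinically significant values are adverse events and are tabulated by treatment. However, 9.4.2 keeps subject-level listings out of the main report body, so the shift table is what stands there.
- *36 of 48 measures the missed shifts.* It measures only where the row is redundant, and it follows from the lab schedule and the period boundaries.

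Other points stand in part. Symptom-driven draws are unevenly ascertained, but excluding them does not even out the row: planned draws run 12, 12, 15 and 21. Different rules for baseline and worst case are defensible in themselves. The SAP does not say whether an extra draw while a subject is in the unit counts as an unscheduled visit, although it mentions unscheduled readings only for listings. The standard shell for these tables is not reproduced, so the handling of follow-up in it cannot be checked. If follow-up were not counted under a treatment, the repetition would extend to all 36 + 12 = 48 subject-periods.

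**Conclusion.** The point holds as a low-priority reporting gap. A blanket exclusion, sound for by-visit summaries, defeats the purpose of the worst-case row. For completers the row repeats the 72 hr row in 36 of 48 subject-periods, including every one at 60 mg and 120 mg, and it omits any valid abnormality seen only at an unscheduled draw. The counts rest on 12 completers without replacements and on the period boundaries in SAP 9.3.1. A subject who withdraws early has follow-up labs as well and could contribute a second scheduled value.

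The effect is confined to the by-dose shift counts in Tables 2.7 and 2.10. The number of missed shifts cannot be estimated from the documents and may be zero.

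**What to change.** In SAP 9.4.2 and 7.2.1, state:

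*Worst-case and any-visit post-baseline rows use all valid individual post-dose values of the same period, scheduled and unscheduled, without averaging under 9.5.1; results invalidated for technical sample problems are excluded. By-visit summaries use scheduled values only.*

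Footnote Tables 2.7 and 2.10 to say that unscheduled draws are symptom-driven or repeats, and that follow-up labs fall in Period 4. Show the actual number of post-dose draws per treatment. Planned counts would be wrong after any withdrawal or replacement.

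The cost is a short insertion in two places, one footnote and minor programming. The downside is that the rows may gain a few shifts from unevenly ascertained draws, which the footnote discloses.

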#### 9.4.3. Reporting Standards for Pharmacokinetic

Pharmacokinetic Concentration Data	
PC Windows Non-Linear (WNL) File	PC WNL file (CSV format) for the non compartmental analysis by Clinical Pharmacology Office function will be created according to GUI_51487. Note: Concentration values will be imputed as per GUI_51487
Descriptive Summary Statistics, Graphical Displays and Listings	Refer to IDSL PK Display Standards. Refer to IDSL Statistical Principle 6.06.1. Note: Concentration values will be imputed as per GUI_51487 for descriptive summary statistics/analysis and summarized graphical displays only.
Pharmacokinetic Parameter Derivation	
PK Parameter to be Derived by Programmer	The following PK parameters will be derived by the Programmer: [C0, C7, C14, C24]
Pharmacokinetic Parameter Data	
Is NQ impacted PK Parameters Rule Being Followed	Yes, refer to GUI_51487.
Descriptive Summary Statistics, Graphical Displays and Listings	Refer to IDSL PK Display Standards. Refer to [Insert document name]

## 9.5. Appendix 5: Derived and Transformed Data

### 9.5.1. General

Multiple Measurements at One Analysis Time Point	

 
Mean of the measurements will be calculated and used in any derivation of summary statistics but if listed, all data will be presented.
 
Participants having both High and Low values for Normal Ranges at any post-baseline visit for safety parameters will be counted in both the High and Low categories of “Any visit post-baseline” row of related summary tables. This will also be applicable to relevant Potential Clinical Importance summary tables.
 
	
Study Day	

 
Calculated as the number of days from First Dose Date: 
 
Ref Date = Missing → Study Day = Missing
 
Ref Date < First Dose Date → Study Day = Ref Date - First Dose Date
 
Ref Date ≥ First Dose Date → Study Day = Ref Date - (First Dose Date) + 1
 
 
 
	
Period Day	

 
Calculated as the number of days from Dosing Date in each period. For study phase derivation, see Appendix 3. 
 
If Study Phase of Ref Assessment or Event = Pre-Treatment or Missing → Period Day = Missing
 
If Study Phase of Ref Assessment or Event = Period X and Ref Date is on or after Dosing Date in Period X → Period Day = Ref Date - Dosing Date in Period X + 1 day
 
If Study Phase of Ref Assessment or Event = Period X and Ref Date is before Dosing Date in Period X → Period Day = Ref Date - Dosing Date in Period X
 
 
 
 
Note: X takes a value of 1, 2, 3, 4.
	

### 9.5.2. Study Population

Age	

 
GSK standard IDSL algorithms will be used for calculating age where birth date will be imputed as follows: 
 
A date and month will be imputed as ‘30th June’ as it will not be captured.
 
 
 
Date of Informed Consent will be used as reference date of calculation.
 
	

### 9.5.3. Safety

Laboratory Parameters
Imputation

• If a laboratory value which is expected to have a numeric value for summary purposes, has a non-detectable level reported in the database, where the numeric value is missing, but typically a character value starting with '<x' or '>x' (or indicated as less than x or greater than x in the comment field) is present, the number of significant digits in the observed values will be used to determine how much to add or subtract in order to impute the corresponding numeric value.

○ Example 1: 2 Significant Digits = '< x' becomes <math>x - 0.01</math>

○ Example 2: 1 Significant Digit = '> x' becomes <math>x + 0.1</math>

○ Example 3: 0 Significant Digits = '< x' becomes <math>x - 1</math>

• The default convention for reporting of clinical laboratory units will be the international system of units (SI units).

## 9.6. Appendix 6: Reporting Standards for Missing Data

### 9.6.1. Premature Withdrawals

Element	Reporting Detail
General	
 
Subject study completion (i.e. as specified in the protocol) was defined as completion of all phases of the study including the last visit or the last scheduled procedure.
 
Withdrawn subjects may be replaced in the study.
 
All available data from participants who were withdrawn from the study will be listed and all available planned data will be included in summary tables and figures, unless otherwise specified.
 
Withdrawal visits will be slotted as per Appendix 3: Assessment Windows or will be summarised as withdrawal visits.
 

### 9.6.2. Handling of Missing Data

Element	Reporting Detail
General	
 
Missing data occurs when any requested data is not provided, leading to blank fields on the collection instrument: 
 
These data will be indicated by the use of a "blank" in subject listing displays. Unless all data for a specific visit are missing in which case the data is excluded from the table.
 
Answers such as "Not applicable" and "Not evaluable" are not considered to be missing data and should be displayed as such.
 
 
 

Outliers	
 
Any participants excluded from the summaries and/or statistical analyses will be documented along with the reason for exclusion in the clinical study report.
 

#### 9.6.2.1. Handling of Missing and Partial Dates

Element	Reporting Detail
General	
 
Partial dates will be displayed as captured in subject listing displays.
 

Adverse Events	
 
The eCRF allows for the possibility of partial dates (i.e., only month and year) to be recorded for AE start and end dates; that is, the day of the month may be missing.
 
The eCRF allows for the possibility of missing times to be recorded for AE start and end dates. Missing dates will be imputed using the following convention: 
 
If the missing time is a start date, a '00:00' will be used for the time.
 
If the missing date is a stop date, a '23:59' will be used for the time.
 
 
 
The recorded missing time will be displayed in listings without imputed values.
 

Concomitant Medications/ Medical History	
 
Partial dates for any concomitant medications recorded in the CRF will be imputed using the following convention: 
 
If the partial date is a start date, a '01' will be used for the day and 'Jan' will be used for the month
 
If the partial date is a stop date, a '28/29/30/31' will be used for the day (dependent on the month and year) and 'Dec' will be used for the month.
 
 
 
The eCRF allows for the possibility of missing times to be recorded for concomitant medications start and end dates. Missing dates will be imputed using the following convention: 
 
If the missing time is a start date, a '00:00' will be used for the time.
 
 
 

Element	Reporting Detail
	

○ If the missing date is a stop date, a '23:59' will be used for the time.

● The recorded partial date and missing time will be displayed in listings without imputed values.

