9.1.1. Time Period and Frequency for Collecting AE and SAE Information

- All SAEs will be collected from the signing of the ICF until the follow-up visit at the time points specified in the SoA (Section 2).
- All AEs will be collected from the start of treatment until the follow-up visit at the time points specified in the SoA (Section 2).
- Medical occurrences that begin before the start of study treatment but after obtaining informed consent will be recorded on the Medical History/Current Medical Conditions section of the CRF not the AE section.
- All SAEs will be recorded and reported to the GSK or designee immediately and under no circumstance should this exceed 24 hrs, as indicated in Appendix 4. The

investigators will submit any updated SAE data to the GSK within 24 hrs of it being available.

- Investigators are not obligated to actively seek AEs or SAEs in former study participants. However, if the investigators learns of any SAE, including a death, at any time after a participant has been discharged from the study, and he/she considers the event to be reasonably related to the study treatment or study participation, the investigators must promptly notify the GSK.
- The method of recording, evaluating, and assessing causality of AEs and SAEs and the procedures for completing and transmitting SAE reports are provided in Appendix 4.

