### Model Specification

- Dose proportionality for AUC(0-24), AUC(0-7) and Cmax following the first (morning) dose will be assessed by using a power model as described below:

$$\log_e (Y_{ij}) = \mu + S_i + \beta * \log_e (D_j) + \varepsilon_{ij}$$

$Y_{ij}$ : PK parameter (AUC(0-24), AUC(0-7), Cmax) on dose j for subject i

$\mu$ : Overall mean (intercept)

$\beta$ : slope for  $\log_e$  transformed dose

$S_i$ : random effect for subject i following normal distribution  $N(0, \sigma_b^2)$

$D_j$ : dose effect ( $j = 60$  mg,  $120$  mg,  $240$  mg)

$\varepsilon_{ij}$ : random error following normal distribution  $N(0, \sigma_w^2)$

- The model parameters will be estimated using Restricted Maximum Likelihood with the Newton-Raphson algorithm.
- The Kenward-Roger degree of freedom approach will be used.

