#### 9.3.1.1. Study Phases for Adverse Events

Study Phase	Definition
Pre-Treatment	AE Onset Date and Time $<$ Study First Dosing Date and Time
Period 1	Dosing Date and Time in Period 1 $\leq$ AE Onset Date and Time $<$ Dosing Date and Time in Period 2
Period 2	Dosing Date and Time in Period 2 $\leq$ AE Onset Date and Time $<$ Dosing Date and Time in Period 3
Period 3	Dosing Date and Time in Period 3 $\leq$ AE Onset Date and Time $<$ Dosing Date and Time in Period 4
Period 4	Dosing Date and Time in Period 4 $\leq$ AE Onset Date and Time
Time since Study First Dose (min)	If study phase of the event is pre-treatment, AE Onset Date and Time - Study First Dosing Date and Time 1 otherwise AE Onset Date and Time – Study First Dosing Date and Time + 1 min
Time since Period First Dose (min)	If study phase of the AE is pre-treatment, set to missing If study phase of the AE is period 1, AE Onset Date and Time – Dosing Date and Time in Period 1 + 1 min If study phase of the AE is period 2, AE Onset Date and Time – Dosing Date and Time in Period 2 + 1 min If study phase of the AE is period 3, AE Onset Date and Time – Dosing Date and Time in Period 3 + 1 min If study phase of the AE is period 4, AE Onset Date and Time – Dosing Date and Time in Period 4 + 1 min
Time since Last Dose (min)	If study phase of the AE is pre-treatment, set to missing If study phase of the AE $\geq$ Study Last Dosing Start Date and Time, AE Onset Date and Time – Study Last Dosing Start Date and Time+ 1 min
Duration (min)	AE Resolution Date and Time – AE Onset Date and Time + 1 min
Drug-related	If relationship is marked 'YES' on eCRF or value is missing.

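### The SAP's 00:00 rule for a missing AE start time, read with its period definitions, takes an untimed dosing-day AE off that day's treatment, and no rule says otherwise

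*SAP*

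**What the plan says.** Several parts of the SAP bear on where an untimed AE is placed.

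- **Imputation (SAP 9.6.2.1).** Blank times are expected: "The eCRF allows for the possibility of missing times to be recorded for AE start and end dates". For a start, "If the missing time is a start date, a '00:00' will be used for the time". Listings show the time as missing; nothing exempts the period derivation from the imputed value.
- **AE periods (SAP 9.3.1.1).** Placement is by date and time. Period 2, for example, is "Dosing Date and Time in Period 2 $\leq$ AE Onset Date and Time $<$ Dosing Date and Time in Period 3". Anything before the study's first dose is Pre-Treatment.
- **Note under that table.** "Time of study treatment dosing and start/stop time of AEs should be considered, if collected".
- **General phase rule (SAP 9.3.1).** "Assessments and events will be classified according to the time of occurrence relative to the date of dosing date". Each period starts on the day before dosing.
- **Concomitant medication (SAP 9.3.1.2).** A missing start time also becomes 00:00, but the comparison is with the dosing date alone: "Dosing Date in Period 1 ≤ Start Date and Time < Dosing Date in Period 2".
- **Display groups (SAP 5.1, 7.1.1).** AE tables count subjects by treatment: placebo, 60 mg, 120 mg and 240 mg. Pre-Treatment is not a display group.

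On collection, Protocol 9.1.1 takes non-serious AEs only from the start of treatment. Earlier occurrences "will be recorded on the Medical History/Current Medical Conditions section of the CRF not the AE section".

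**The concern.** In this crossover the period decides the AE's column. A midnight onset on a dosing day precedes a morning dose, so 9.6.2.1 and 9.3.1.1 together credit the AE to whatever the subject took the period before. Because doses ascend within each sequence, an AE on an active day always moves to a lower active dose, to placebo or to Pre-Treatment. An AE on a placebo day moves to an active dose in 9 of 12 subject-periods.

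The result conflicts with the rest of the plan in three ways:

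- The note under the AE table and the general phase rule both point to placement by date, which moves nothing.
- An untimed AE and an untimed medication given for it on the same day would fall in different periods.
- A non-serious AE dated Period 1 Day 1 should not be pre-treatment under Protocol 9.1.1, yet the rule labels it so.

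AEs are the first-listed safety endpoint. Protocol 10.4.1 leaves comparison with placebo to descriptive summaries, here in columns of 12. Two programmers following this SAP could produce different AE tables.

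**Working it through.** **Inputs.** Four sequences of 3 subjects over 4 periods (SAP 2.3): 4 x 4 x 3 = 48 subject-periods, 12 per treatment. Doses are at 0, 7 and 14 hr on Day 1, with breakfast about 2 hr after the first (Protocol 5.1). SAP 8.1.5.1 describes parameters "following the first (morning) dose". The clock time is not stated. For the third dose to fall on the same calendar day, the first must be before 24 - 14 = 10:00. Any first-dose time after 00:00 gives the same placement; 01:00, 06:00, 08:00 and 09:59 were tried.

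**The plan's own figures.** There is none for this rule. Protocol 10.1 gives exact 95% upper limits of 26.5% for 0/12 and 38.5% for 1/12. Both reproduce: for 0/12, 1 - 0.025^(1/12) = 0.265. Moving one subject out of a column with a single event therefore changes 8.3% (limit 38.5%) to 0% (limit 26.5%).

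**Step 1: where each subject-period goes.** An untimed AE on the dosing day of Periods 1, 2, 3 and 4 goes to Pre-Treatment, Period 1, Period 2 and Period 3.

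| True treatment | to Pre-Treatment | to placebo | to 60 mg | to 120 mg | to 240 mg | lost |
|---|---|---|---|---|---|---|
| Placebo | 3 | – | 3 | 3 | 3 | 12 |
| 60 mg | 9 | 3 | – | 0 | 0 | 12 |
| 120 mg | 0 | 3 | 9 | – | 0 | 12 |
| 240 mg | 0 | 3 | 0 | 9 | – | 12 |
| **gained** | 12 | 9 | 12 | 12 | 3 | 48 |

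Of 36 active subject-periods, 18 go to a lower active dose, 9 to placebo and 9 to Pre-Treatment. Net change is -9 for 240 mg, -3 for placebo and 0 for 60 mg and 120 mg. Under date-only placement nothing moves.

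**Step 2: bias.** Let p_T be the dosing-day AE rate on treatment T and m the fraction of those AEs with no start time. The documents give neither, so both are assumptions.

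Expected observed rate = (1 - m) p_T + m x (sum of inflow subject-periods x source rate) / 12

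*Equal rates p:*

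- 240 mg: (1 - m)p + 3mp/12 = p - 0.75mp
- Placebo: (1 - m)p + 9mp/12 = p - 0.25mp
- 60 mg and 120 mg: (1 - m)p + 12mp/12 = p
- Bias in the difference from placebo: -0.5mp for 240 mg, +0.25mp for 60 mg and 120 mg

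*Dose-related rates of 1/12, 1/12, 2/12 and 4/12 (placebo, 60, 120, 240 mg):*

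- 240 mg: inflow 3 x (1/12)/12 = 0.25/12, so the change is -m(4 - 0.25)/12 = -3.75m/12
- Placebo: inflow 3 x (1 + 2 + 4)/12/12 = 1.75/12, so the change is +m(1.75 - 1)/12 = +0.75m/12
- Bias in 240 mg minus placebo: -4.5m/12 = -0.375m, against a true difference of 3/12 = 25 points

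| m | 240 mg - placebo, p = 25% | 60 or 120 mg - placebo, p = 25% | 240 mg - placebo, dose-related |
|---|---|---|---|
| 5% | -0.6 points | +0.3 | -1.9 |
| 10% | -1.25 | +0.6 | -3.75 |
| 20% | -2.5 | +1.25 | -7.5 |

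The tables count subjects, so an AE arriving in a column where that subject already has the same preferred term adds nothing. The inflows are therefore upper bounds.

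**Step 3: does date-only placement resolve everything?** Not if the imputed time is still used elsewhere. SAP 9.3.1.1 derives time since the period's first dose as onset minus dosing time plus 1 min. With a 00:00 onset and an assumed 08:00 dose that is -480 + 1 = -479 min.

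**The case against.** The strongest reply is that the note under the AE table already covers this case: with no time collected, compare dates, and nothing moves. The general phase rule agrees. SAP 9.6.2.1 never says its imputed time feeds period assignment, and the 00:00 and 23:59 values have another use, the AE duration in minutes. This is a fair reading. It is not the only one: the note may mean whether the study collects AE times at all, which it does, with blanks allowed. No section gives it precedence, and Step 3 shows that it leaves a derived variable wrong.

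On size, the 48 are subject-periods at risk, not events. At p = 25% and m = 5% or 10%, 48 x 0.25 x m is 0.6 or 1.2 AEs misplaced in the whole trial. The largest bias shown, -7.5 points, is 0.9 of a subject in a column of 12 and needs 20% of times missing and an assumed dose-response. Subjects are in-house from the day before dosing to 72 hr, so m is probably low. Affected records can be found in the listings, and escalation rests on the blinded review at each period. All of this stands and limits the severity.

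Two smaller points also stand. A fully timed pre-dose AE and medication in Periods 2 to 4 would split across periods too, so the medication mismatch alone does not prove the AE rule wrong. And imputing the first-dose time would make the opposite error for an untimed AE that truly began before that morning's dose, so the fix needs an exception.

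**Conclusion.** The concern holds. As written, the imputation and the period definitions together put an untimed dosing-day AE in the wrong treatment column or in none, and the SAP does not say that the date-only note overrides them. The two rules do not conflict with each other; their combined result conflicts with the note, the general phase rule and the protocol's AE collection window.

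The distortion is not one-directional. At equal rates it lowers 240 mg most, lowers placebo slightly and leaves 60 mg and 120 mg unchanged, for a bias of -0.5mp in 240 mg minus placebo. It is zero under the date-only reading. Every percentage-point figure rests on assumed values of p and m; the placement counts rest only on the design and a first dose after midnight. The number of AEs affected is unknown and probably small, and only the final by-treatment AE tables are touched, including the drug-related ones. It should be fixed before unblinding, but it does not threaten the trial.

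**What to change.** State one rule that reconciles SAP 9.3.1.1, its note and 9.6.2.1: an AE with a missing start time, dated on a dosing date, is assigned to that day's period by imputing that period's first-dose time, unless recorded information shows it began or ended before that dose. Keep 00:00 for untimed AEs on other dates. This agrees with the date-level comparison already used for concomitant medication and removes the negative time since first dose.

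Flag imputed onset times in Listing 14. The listing will already show the time as blank; the flag tells the reader that the period came from the rule.

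Cost: one sentence in the SAP, one line of derivation code, one listing flag, and a blinded look at the probably few affected records to apply the pre-dose exception. No study procedure changes.
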